Pain is an undesirable consequence of surgery especially cardiac surgery as pain during and following cardiac surgery has been shown to be a risk factor for increased morbidity. Systemic opioids have been the main stay for the management of perioperative pain in cardiac surgery. Lower doses of opioids has been related to early extubation and minimizing opioid-related side effects, such as prolonged ventilation, tolerance, nausea, vomiting, gut dysfunction, and immunosuppression.

On the other hand we find cases of morbidity and mortality not related to the surgical procedure. ERAS protocol discuss the optimum condition that can we use to avoid the morbidity and mortality complications.

We aim to know how well ERAS protocol is known and applied

Aim of the work

Our aim is to know how well cardiac anesthesiologists, cardiac intensivists and cardiothoracic surgeons know and apply ERAS protocol in mitral valve surgery.

Objectives:

We will use the questionnaire about ERAS guidelines to assess the knowledge of doctor about the guidelines.

Hypothesis:

Our hypothesis is that ERAS guidelines are not well known among doctors.

Ethical Considerations

The study will be conducted after taking approval of the research and ethical committees.

Informed consent will be obtained from study participants or their legally authorized representative.

Methodology

I. Study design

Cross section study to assess of knowledge about Enhance Recovery After Surgery (ERAS) guidelines between cardiac anesthesiologists, cardiac intensivists and cardiothoracic surgeons.

II. Study setting and location

- Anesthesia department, Cairo university hospitals, kasr al-ainy.
- Cardiothoracic thoracic surgery department, Cairo university hospitals, kasr al-ainy.
- Anesthesia department, National Heart Institute.
- Cardiothoracic surgery department, National Heart Institute.

III. Study population

- Cardiac anesthesiologists
- Cardiac intensivists
- Cardiothoracic surgeons

IV. Eligibility Criteria

1. Inclusion criteria

- Cardiac anesthesiologists.
- Cardiac intensivists.
- **Cardiothoracic surgeons.**
- All staff members from resident to consultant are included inside this study

V. Study Procedures

1. Randomization (in RCT only)

A questionnaire **will be sent online** to a random sample of anesthesiologists and intensive care physicians.

The random sample will be taken by use of random list.

2. Study Protocol:

The questionnaire consists of number of questions that the doctor has to answer in a set format. It will be a closed-ended questions:-

- Dichotomous
- Nominal-polytomous
- Ordinal-polytomous

Grading system will be described as:-

- Grade A (knows well (: more than 60 % correct answer
- Grade B (fair): 35 :60 % correct answer
- Grade C (knows nothing) :- less than 35 % correct answer

2. Measurement tools

1. Questions about ERAS society
2. Questions about premedications
3. Questions about opioids
4. Questions about ERAS guidelines :-
 - Preoperative Hb A_{1c} measurement
 - Preoperative measurement of Albumin
 - Preoperative correction of nutritional deficiency
 - Consumption of clear liquid before GA
 - Preoperative carbohydrates loading
 - Prehabilitation

VI. Study outcomes

1. Primary outcome

Assesment of the knowledge of doctors to ERAS guidelines in cardiac surgery by using the grading system.

2. Secondary outcome(s)

Statistical Analysis

I. Sample size

The sample size had determined using epi-infoVersion 7 based on the following prerequisites:

- Confidence level = 95%
- Expected frequency of knowledge about Enhance Recovery After Surgery (ERAS) guidelines between cardiac anesthesiologists, cardiac intensivists and cardiothoracic surgeons = 50%.

- Confidence limit =5%

- Population size = 1000 (cardiac anesthesiologists, cardiac intensivists and cardiothoracic surgeons in Cairo University hospitals (Koir Al Ainy) and National Heart Institute).

This gave a minimum sample size two hundred and seventy eight physicians had selected to be included in the study.

II. Statistical analysis

The collected data will be revised, coded and analyzed using SPSS version 21 software for tabulation and analysis.

The following statistical measures will be calculated:

A. Descriptive statistics:

1- Count and percentage.

2- For quantitative variables, arithmetic mean and standard deviation will be calculated.

B. Analytical statistics:

The data will be analyzed and when $p<0.05$ will be considered statistically significant.

References

[1] Scott MJ, Baldini G, Fearon KC, Feldheiser A, Feldman LS, Gan TJ, Ljungqvist O, Lobo DN, Rockall TA, Schricker T, Carli F. Enhanced Recovery After Surgery (ERAS) for gastrointestinal

surgery, part 1: pathophysiological considerations. Acta Anaesthesiol Scand. 2015 Nov;59(10):1212-31. doi: 10.1111/aas.12601. Epub 2015 Sep 8. PMID: 26346577; PMCID: PMC5049676.

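### The sampling sentence drops the cardiac restriction that defines the target population, and nothing described in the plan restores it

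*Combined protocol and SAP*

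**What the plan says.** Most of the combined protocol and SAP restricts the study to three cardiac groups, from anesthesia, intensive care and surgery. The aim, the study design, the study population (Methodology III) and the inclusion criteria (Methodology IV) all do this. So does the sample size section, which gives "Population size = 1000 (cardiac anesthesiologists, cardiac intensivists and cardiothoracic surgeons in Cairo University hospitals" and the second institution, and attaches the expected frequency of 50% to the same groups.

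The operational text is looser:

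- Study Procedures, item 1 (Randomization), sends the online questionnaire "to a random sample of anesthesiologists and intensive care physicians". The word cardiac is absent, and surgeons are not mentioned. The next line says a random list will be used but not where it comes from.
- Study setting and location (Methodology II) lists four departments. Two are cardiothoracic surgery departments and one is the anesthesia department of a heart institute. The fourth is "Anesthesia department, Cairo university hospitals, kasr al-ainy".
- The inclusion criteria add "All staff members from resident to consultant are included inside this study", without saying what makes a doctor of any grade cardiac.
- Measurement tools lists four blocks of questions: the ERAS society, premedication, opioids and guideline items. None is described as recording specialty or cardiac practice.

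**The concern.** A survey proportion describes the population from which its list was drawn. Here the document that defines eligibility and the sentence that produces the sample name different populations, and the plan gives the person building the list no rule for deciding between them. The exposure is mainly in two places: the university hospital anesthesia department, which is listed without a cardiac qualifier, and the unqualified mention of intensive care physicians.

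If non-cardiac doctors are sampled and answer, the reported figure is a mixture of cardiac and non-cardiac knowledge in unknown proportions. The precision statement would no longer apply to cardiac staff. A larger sample does not help, because the error lies in who is counted. If the form does not record cardiac involvement, separating the two groups after data collection depends on information the plan does not say will be kept.

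**Working it through.** **Inputs from the plan (Statistical Analysis, I. Sample size).** Confidence level 95% (z = 1.96), expected frequency p = 0.50, confidence limit d = 0.05, population N = 1000, stated minimum sample 278.

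**Step 1: reproduce the plan's figure.**

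n0 = z² p(1−p) / d² = 1.96² × 0.25 / 0.0025 = 384.16

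n = n0 / (1 + (n0 − 1)/N) = 384.16 / 1.38316 = 277.74, rounded up to 278

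The figure reproduces. The half-width with n = 278 and N = 1000 is 1.96 × √[(0.25/278) × (722/999)] = 0.050, or 5.0 points. This calculation is not in dispute, but it is valid for a random sample of the 1000 cardiac staff and for no other population.

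**Step 2: effect of a mixed sample on the estimate.** Let f be the share of respondents who are non-cardiac and q the proportion of them classed as having the knowledge. The plan gives neither, so both are assumptions. The true cardiac value is set at the plan's own 50%.

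Expected estimate = 0.50(1 − f) + q f, so bias = f(q − 0.50)

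| Non-cardiac share f | q = 25% | q = 50% | q = 70% |
|---|---|---|---|
| 10% | 47.5% | 50% | 52% |
| 20% | 45% | 50% | 54% |
| 40% | 40% | 50% | 58% |

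For example, at f = 20% and q = 25%: 0.50 × 0.80 + 0.25 × 0.20 = 0.45. At f = 20% and q = 70%: 0.40 + 0.14 = 0.54. The sign of the bias is the sign of q − 0.50, which the plan does not determine.

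**Step 3: effect on precision if non-cardiac forms are set aside.** With f = 20%, 278 × 0.80 = 222.4 eligible forms remain. The result depends on what the 1000 really counts:

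- If the 1000 itself contains the same share of non-cardiac doctors, the cardiac population is 800. The half-width is 1.96 × √[(0.25/222.4) × (577.6/799)] = 0.056, or 5.6 points.
- If the 1000 are all cardiac and the list was drawn more widely, the half-width is 1.96 × √[(0.25/222.4) × (777.6/999)] = 0.058, or 5.8 points.

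The loss of precision is modest. The larger issue is Step 2, which cannot be bounded without knowing who answered.

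**The case against.** The strongest reply is that eligibility criteria, not a site list or a loosely worded sentence, decide who may be counted. Those criteria name cardiac groups. The only population the plan enumerates is the 1000 cardiac staff, so the random list may well be drawn from exactly that roster. The line on grades follows the cardiac groups and most naturally widens seniority, not specialty. This stands as far as it goes: a reader might infer that the plan has no cardiac restriction at all, and that is wrong. It does not settle the matter, because the sampling sentence says something else, the list source is not given, and an undefined criterion with no described check does not enforce itself in an online questionnaire.

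Four further inferences are tempting but not supported:

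- **That the sampling frame is whole anesthesia departments.** The document states where the study takes place, not what list is used. Two of the four sites are cardiothoracic surgery departments, and one of the two anesthesia departments belongs to a heart institute.
- **That any dilution favours the hypothesis of poor knowledge.** The listed guideline items (HbA1c, albumin, nutrition, clear fluids, carbohydrate loading, prehabilitation) are general perioperative topics, and the plan's first reference concerns ERAS in gastrointestinal surgery. Non-cardiac doctors might score as well or better.
- **That the absence of a listed intensive care unit adds to dilution.** At most it raises a question of coverage. Cardiac intensivists may belong to a listed department; the document does not say.
- **That ineligible respondents could never be removed.** The questionnaire itself is not in the document, and respondents might be checked against the list. The plan is silent on both.

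**Conclusion.** The point holds in a limited form. The sampling sentence is inconsistent with the cardiac-only aim, inclusion criteria and population of 1000, and the plan describes no list source, no definition of cardiac practice and no eligibility item that would resolve the inconsistency. Followed literally, the rule can admit doctors outside the target population, and the 278 and ±5 points would then not describe the cardiac staff for whom they were computed.

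Whether this will happen, how much, and in which direction it would move the result cannot be derived from the document. At an assumed 20% non-cardiac share and a true cardiac value of 50%, the estimate runs from 45% to 54% as assumed non-cardiac knowledge runs from 25% to 70%. The lower end is an error as large as the whole planned confidence limit; with equal knowledge there is no error. These are illustrations, not predictions.

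The change should be made because it is cheap before launch and protects the study's ability to answer its own question. It does not depend on showing that a bias exists.

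**What to change.** 1. Reword the sampling sentence in Study Procedures so that it names the same eligible cardiac groups as the inclusion criteria, surgeons included.
2. State the source of the random list, and make it the roster of cardiac staff that defines the population of 1000. If the roster gives a different count, restate N and recompute. For example, a roster of 800 would need 384.16 / (1 + 383.16/800) = 259.8, that is 260 respondents, by the plan's own formula.
3. State which units the cardiac intensivists are recruited from.
4. Define in advance what counts as current involvement in cardiac surgery care. The investigators should set the definition.
5. Open the form with short items on specialty, rank, institution and that involvement. If such items already exist, list them under Measurement tools.
6. Limit the primary analysis to eligible respondents, and report how many returned forms were set aside.

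The cost is a wording change, a roster check and a few opening questions. The downside is small: the eligible list may be shorter than 1000, and some returned forms will fall outside the primary analysis.

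### The sentence that says who is sent the questionnaire omits cardiothoracic surgeons, although the aim, eligibility criteria and the population of 1000 behind n = 278 include them

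*Combined protocol and SAP*

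**What the plan says.** Under Study Procedures, item 1 (Randomization), the questionnaire goes online "to a random sample of anesthesiologists and intensive care physicians". The following sentence adds only the mechanism: "The random sample will be taken by use of random list". It does not say whom the list covers.

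Elsewhere the combined protocol and SAP defines the target population as three groups:

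- Statement of the aim: "Our aim is to know how well cardiac anesthesiologists, cardiac intensivists and cardiothoracic surgeons know and apply ERAS protocol in mitral valve surgery".
- Study design: "Cross section study to assess of knowledge about Enhance Recovery After Surgery (ERAS) guidelines between cardiac anesthesiologists, cardiac intensivists and cardiothoracic surgeons".
- Study population and inclusion criteria: cardiothoracic surgeons have their own bullet under both headings, and the criteria take in every grade of staff.
- Study setting: two cardiothoracic surgery departments are sites, one of them listed as "Cardiothoracic surgery department, National Heart Institute".
- Sample size, expected frequency: "Expected frequency of knowledge about Enhance Recovery After Surgery (ERAS) guidelines between cardiac anesthesiologists, cardiac intensivists and cardiothoracic surgeons = 50" percent.
- Sample size, population: "Population size = 1000 (cardiac anesthesiologists, cardiac intensivists and cardiothoracic surgeons in Cairo University hospitals" and the National Heart Institute.

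**The concern.** The sampling sentence is the operational one: whoever builds the mailing list works from it. It names two of the three target groups, and no other text gives surgeons a route into the sample. Read literally, no surgeon would be invited.

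Two things would follow. The aim could not be answered for one of the three groups it names. The pooled percentage in each knowledge grade, which is the primary outcome, would describe a narrower population than the 1000 physicians on whom the sample size rests. This is a coverage error, so a larger sample does not shrink it, and analysis cannot recover a group that was never invited.

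**Working it through.** **1. Inputs from the Sample size section.** Confidence level 95% (z = 1.96), expected frequency p = 0.50, confidence limit d = 0.05, population N = 1000 across all three groups, stated minimum n = 278.

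**2. Reproducing the plan's figure.** For a single proportion with finite population correction:

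n = N·p(1−p) / [(d²/z²)(N−1) + p(1−p)]

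= 1000 × 0.25 / [(0.0025/3.8416) × 999 + 0.25] = 277.7, rounded up to 278.

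The stated figure reproduces, so the calculation already counts surgeons in the sampling frame.

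**3. What the sample size would be without surgeons.** The number of surgeons is not given, so the share is an assumption. Each N below goes into the same formula.

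| Assumed surgeon share | N without surgeons | n required |
|---|---|---|
| 10% | 900 | 270 |
| 20% | 800 | 260 |
| 30% | 700 | 249 |
| 40% | 600 | 235 |
| 50% | 500 | 218 |

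The sampling sentence and the stated population therefore cannot both stand.

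**4. Precision.** Suppose 278 physicians are drawn from the two named groups only. The half-width is 1.96 × √[(0.25/278) × (N−278)/(N−1)]. This is 4.9 points at N = 900 and 3.9 points at N = 500. The confidence interval would still meet the 5-point limit and would give no warning that a group was missing.

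**5. Surgeons expected under the intended design.** In a simple random sample of 278 from all 1000, the expected number is share × 278: 0.10 × 278 = 27.8, 0.25 × 278 = 69.5 and 0.40 × 278 = 111.2. That is about 28 to 111 surgeons, against none under the literal rule.

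**6. Coverage bias.** Let s be the surgeon share, P_S the percentage of surgeons in a given grade, and P_O the same percentage in the other two groups. The target is (1−s)·P_O + s·P_S, while the literal rule estimates P_O. The difference is s × (P_O − P_S), that is, share × gap. The gap is not given either; 0 to 20 points is assumed.

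| Share | Gap 0 | Gap 10 | Gap 20 | Gap at which bias reaches 5 points (5/share) |
|---|---|---|---|---|
| 10% | 0 | 1 | 2 | 50 |
| 25% | 0 | 2.5 | 5 | 20 |
| 40% | 0 | 4 | 8 | 12.5 |

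All entries except the share are percentage points. The plan does not say which grade its 50% refers to; the formula applies to the percentage in any grade. It assumes that the frame actually used is exactly the cardiac anesthesiologists and cardiac intensivists among the 1000.

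**The case against.** The strongest reply is that the documents leave little doubt about who is meant. Surgeons appear in every definition of the population, and one sentence, under a template heading meant for randomised trials, is out of step. The content of the random list is not specified, so nothing proves that surgeons are off it. A drafting slip is quite possible. Even so, the reader has to infer the intent against the only explicit sampling instruction, and the error could not be undone once the survey closes.

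Several narrower points stand:

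- **The sites.** They are weak evidence, because intensivists may work in a cardiothoracic surgery department. The contradiction does not depend on them.
- **The word cardiac.** The sampling sentence drops this qualifier as well, so read strictly it reaches anesthesiologists and intensive care physicians in general. That is a second mismatch in the same sentence, and the simple bias formula sets it aside.
- **The size of the bias.** Both inputs are assumed. Of the nine combinations tabulated, one exceeds 5 points, one equals it and three are zero. The table shows what could happen; it does not show that material bias is likely.
- **No analysis by specialty.** The analysis section plans none, so the main statistical harm is to the pooled figure. The aim still names surgeons as a group to be assessed.

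**Conclusion.** The concern holds. The sampling rule contradicts the aim, study design, study population, inclusion criteria and both sample-size inputs that name the target groups. As written, it yields no surgeons. That conclusion rests on the text alone and needs no assumption.

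The size of the resulting bias is conditional: 0 to 8 points over an assumed surgeon share of 10% to 40% and an assumed knowledge gap of 0 to 20 points. It passes the planned 5-point limit only if the gap exceeds 50, 20 or 12.5 points at shares of 10%, 25% and 40%. The arithmetic behind 278 is correct, and precision is not at issue. Because the fault lies in the rule that decides who is studied, it must be corrected before the questionnaire is sent.

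**What to change.** Rewrite the sampling sentence in Study Procedures, item 1, so that the online questionnaire goes to a random sample of cardiothoracic surgeons, cardiac intensivists and cardiac anesthesiologists. This also restores the missing qualifier. Add that the random list is drawn from the combined population of 1000 used in the sample-size calculation. Proportional stratification by specialty and hospital is optional, if the list records them.

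The cost is one sentence and a sampling list that covers all three groups; n stays at 278. If the investigators in fact meant to leave surgeons out, the aim, design, population, criteria, sites and sample-size inputs would all have to change instead, and n would be recalculated from the smaller N, as in step 3 of the working.

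### The 5-point margin behind the sample size of 278 covers sampling error only; the plan has no provision for non-response to a voluntary online knowledge test, which could bias the grade percentages by as much or more

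*Combined protocol and SAP*

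**What the plan says.** **Selection.** V. Study Procedures, 1. Randomization, says that the questionnaire "will be sent online" and that "The random sample will be taken by use of random list". It does not say what the list is, what it records about each doctor, how many will be invited, whether reminders go out, or what happens when a selected doctor does not reply. Ethical Considerations requires informed consent, so a selected doctor may decline.

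**Who is sampled.** The sampling sentence names only anesthesia and intensive care doctors. The study population, the inclusion criteria and the population of 1000 in the sample size section also include cardiothoracic surgeons.

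**Size.** Statistical Analysis, I. Sample size, uses 95% confidence, an expected frequency of 50%, a confidence limit of 5% and a population of 1000. It concludes: "This gave a minimum sample size two hundred and seventy eight physicians had selected to be included in the study". No response rate is given, and the text does not say whether 278 means invited or completed.

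**Analysis.** The primary outcome is knowledge on a three-level grading (A, B, C). For such data, II. Statistical analysis lists "Count and percentage". It contains no response-rate reporting, comparison of responders with the list, weighting or non-response sensitivity analysis.

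**The concern.** The sample size formula describes the error of a percentage when the people analysed are a simple random sample of the population. Random selection gives that property to the doctors invited. It passes to the doctors analysed only if nearly all reply, or if replying is unrelated to what they know.

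Here the outcome is a marked knowledge test and participation is voluntary, so a link between knowledge and willingness to answer is plausible. The deliverable is a description of one population, with no comparison group in which such a bias might cancel. The 5 points cover sampling error and say nothing about this second source of error. Without response rates and a sensitivity range, a reader of the results could not judge how far the percentages apply to the 1000.

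**Working it through.** **1. The plan's own figure.** Inputs from I. Sample size: N = 1000, p = 0.5, d = 0.05, 95% confidence (z = 1.96).

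n = N·p(1−p) / [(d²/z²)(N−1) + p(1−p)] = 250 / (0.650 + 0.25) = 277.7, rounded up to 278. The stated figure is reproduced.

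Half-width at n = 278: 1.96 × √(0.25/278 × 722/999) = 4.997 points. This is the simple-random-sample margin with finite population correction. It contains no term for non-response.

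**2. Non-response bias.** With response rate r:

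bias = (1 − r) × (percentage among responders − percentage among non-responders).

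The number of forms does not appear in it. The gap that gives a 5-point bias is 5/(1 − r). The documents give neither r nor the gap, so both are assumptions over a range:

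| Response rate | Gap giving 5 points of bias | Bias if gap is 10 points | Bias if gap is 20 points |
|---|---|---|---|
| 30% | 7.1 | 7 | 14 |
| 50% | 10 | 5 | 10 |
| 70% | 16.7 | 3 | 6 |
| 80% | 25 | 2 | 4 |
| 90% | 50 | 1 | 2 |

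The signs reverse if non-responders know more.

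**3. The same in terms of who answers.** Suppose 50% truly have the knowledge. If 55% of those who have it answer and 45% of those who do not, the observed figure is 0.275/(0.275 + 0.225) = 55%, a 5-point bias. At 60% v 40% the bias is 10 points; at 80% v 70% it is 3.3 points.

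**4. Effect on an interval of the planned width.** The standard error is 4.997/1.96 = 2.55 points. With a shifted mean and the normal approximation, a nominal 95% interval covers the truth 83% of the time with a 2.5-point bias, 50% with 5 points, 16% with 7.5 points and 2.5% with 10 points.

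**5. What weighting can and cannot do (illustration; all rates assumed).** Take three ranks with staff shares 50/30/20%, response rates 25/45/60% and Grade A rates 25/45/60%.

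- True Grade A: 0.5×0.25 + 0.3×0.45 + 0.2×0.60 = 38.0%.
- Overall response: the same sum, since the two sets of rates were chosen equal, so 0.380.
- Raw figure among responders: (0.5×0.25² + 0.3×0.45² + 0.2×0.60²)/0.380 = 43.2%, which is 5.2 points too high.
- Weighted to staff totals by rank: 38.0%.
- Cost: responder shares are 32.9/35.5/31.6%, so the design effect is 0.50²/0.329 + 0.30²/0.355 + 0.20²/0.316 = 1.14, and 4.997 × √1.14 = 5.3 points.

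Weighting recovers the truth here only because response does not depend on knowledge within a rank. Let Grade A doctors answer 1.22 times as often (55/45) inside each rank. Grade A among responders becomes 28.9%, 50.0% and 64.7% in the three ranks, and the rank-weighted figure is 0.5×0.289 + 0.3×0.500 + 0.2×0.647 = 42.4%. That leaves 4.4 points of bias after weighting.

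**The case against.** The strongest reply is that the bias may be small. If these staff answer at 90%, responders and non-responders would have to differ by 50 points to move the result by 5. The documents do not exclude a response that high. This stands: the calculation shows what can happen, not what will.

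The plan is also less definite than the concern makes it. The primary outcome has three grades, and nothing says which of them counts as knowledge in the 50% used for sizing. The 5% is a sample size input, and the analysis section lists no interval. This stands too, so the point applies to each grade percentage.

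A reader might infer three stronger things that the documents do not support.

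- *That well-informed doctors will answer more, so the result will overstate knowledge and work against the hypothesis.* This is plausible, but nothing in the plan fixes the direction.
- *That department and rank are already held for non-responders, so weighting is ready to use.* The plan mentions only a random list. It does not say whether that is a staff roster or which fields it holds. The named settings are anesthesia and cardiothoracic surgery departments, so department alone would not identify intensivists.
- *That weighting cures the problem.* Step 5 shows that it need not. If the sampling sentence is followed literally, the surgeon cells would be empty, and no weighting can fill them.

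None of this supplies the missing non-response plan.

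**Conclusion.** The gap is real and should be closed before the questionnaire goes out. The figure of 278 is correct for the inputs stated, so this is not a complaint about sample size. Inviting more doctors to reach 278 completed forms would protect precision and leave the bias as it was.

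The size depends on two quantities that the plan does not give. At response rates of 50% to 70%, a difference of about 10 to 17 points between responders and non-responders is enough to equal the whole planned margin. At 80% or above the difference would have to be 25 points or more. A reader might infer that the result will be wrong by more than 5 points; the supported statement is that it could be, in either direction, and that the plan as written gives no means of telling. Confidence is medium, because the gap in the text is clear but the magnitude is assumed.

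**What to change.** **In V. Study Procedures, 1.**

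- First reconcile the sampling sentence with the study population, which includes cardiothoracic surgeons.
- Draw the sample from a staff roster of all three groups. Record department and rank for every selected doctor where the roster holds them.
- Send individual links with at least two reminders.
- Do not replace non-responders with convenient volunteers. If more forms are needed, release a further complete random batch and count all of it in the denominator.

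**In II. Statistical analysis.**

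- Report the response rate overall and by department and rank, and compare responders with the roster.
- Give the grade percentages unweighted and, beside them, post-stratified to roster totals on the fields available, with small cells collapsed.
- Add a two-sided sensitivity range. For each grade in turn, set the percentage among non-responders 10 and 20 points lower and higher than among responders (kept within 0 to 100), and recompute as responder percentage − (1 − r) × gap. At an assumed 50% response this moves the figure by 5 and 10 points each way.

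**Cost.** A few sentences, a weighting step and slightly wider error bars (about 5.0 to 5.3 points in the illustration). Weighting removes only the part of the bias tied to the roster variables, so the sensitivity range is needed for the rest. The sampling and follow-up steps must be settled before the draw, because links and roster data cannot be reliably reconstructed afterwards.

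### The sampling rule states no strata and leaves cardiothoracic surgeons out of the sampling sentence, so the specialty and hospital mix of those invited is left to chance and surgeons may not be invited at all

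*Combined protocol and SAP*

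**What the plan says.** **Sampling.** Section V.1 of the combined protocol and SAP (Study Procedures, Randomization) has two sentences on the draw. The first sends the online questionnaire to a random sample and names two groups, anesthesiologists and intensive care doctors. The second reads "The random sample will be taken by use of random list". Neither describes a staff list, strata or an allocation.

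**Population.** The aim, the study population and the inclusion criteria all name three specialties, including cardiothoracic surgeons. The setting lists the anesthesia and cardiothoracic surgery departments of two institutions. On rank, the inclusion criteria say "All staff members from resident to consultant are included inside this study".

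**Design.** Section I of the Methodology reads "Cross section study to assess of knowledge about Enhance Recovery After Surgery (ERAS) guidelines between cardiac anesthesiologists, cardiac intensivists and cardiothoracic surgeons".

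**Sample size.** The inputs are "Confidence level = 95" (percent), "Expected frequency of knowledge about Enhance Recovery After Surgery (ERAS) guidelines between cardiac anesthesiologists, cardiac intensivists and cardiothoracic surgeons = 50" (percent), "Confidence limit =5" (percent) and "Population size = 1000 (cardiac anesthesiologists, cardiac intensivists and cardiothoracic surgeons in Cairo University hospitals" and the National Heart Institute. The result is given as "This gave a minimum sample size two hundred and seventy eight physicians had selected to be included in the study".

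**Outcome and analysis.** The primary outcome is the knowledge of doctors as a whole, by grade. The secondary outcome field is empty. The analytical section gives a p-value threshold but no test and no grouping factor.

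**The concern.** Two things do not fit together.

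First, the sampling sentence covers two of the three specialties to which the 1000 and the 278 refer. If the list is built from that sentence, the pooled percentage describes anesthesiologists and intensivists but is reported for all three groups. A larger sample does not cure that error.

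Second, even with surgeons on the list, a single simple random draw matches the population's specialty and hospital mix only on average. The one sample actually drawn can be thin in a small specialty. The plan does not say that its ±5 points belongs to the pooled figure alone, so a reader could attach it to a specialty result that is much less precise. Once invitations have gone out, a group left off the list or not recorded on the form cannot be recovered in the analysis.

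**Working it through.** **Inputs from the Sample size section:** N = 1000, p = 0.50, d = 0.05, 95% confidence (z = 1.96), n = 278. **Assumed, because the documents give none:** specialty sizes, knowledge rates by specialty, and a reply from everyone invited.

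**1. The plan's own figure.** For one proportion with finite population correction,

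n = N·p(1−p)·z² / [d²(N−1) + z²·p(1−p)] = 1000 × 0.25 × 3.8416 / (0.0025 × 999 + 0.9604) = 960.4 / 3.4579 = 277.7, rounded up to 278.

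This is the simple-random-sampling formula for one pooled population. The 278 reproduces.

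**2. Pooled half-width as planned.** 1.96 × √(0.25/278 × 722/999) = 0.0500, or 5.0 points. The stated target is met without strata.

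**3. Pooled half-width with proportional strata.** The variance is multiplied by the ratio Σ W_h·p_h(1−p_h) / [p(1−p)]. For three equal specialties with overall p = 0.50:

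- 40/50/60%: (0.24 + 0.25 + 0.24)/3 = 0.2433. Ratio 0.973, half-width 5.0 × √0.973 = 4.9 points.
- 30/50/70%: (0.21 + 0.25 + 0.21)/3 = 0.2233. Ratio 0.893, half-width 4.7 points.
- 20/50/80%: (0.16 + 0.25 + 0.16)/3 = 0.19. Ratio 0.760, half-width 4.4 points.

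**4. Number drawn from a small specialty.** With an assumed 100 of 1000, a simple random draw of 278 takes a hypergeometric number from that specialty. The mean is 278 × 100/1000 = 27.8. The SD is √(278 × 0.1 × 0.9 × 722/999) = 4.25. The 2.5% to 97.5% range is 20 to 36. Proportional allocation fixes the number at about 28.

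**5. Half-width within a specialty of size K,** 1.96 × √(0.25/n × (K−n)/(K−1)):

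- n = 28 of 100: 15.8 points
- n = 20 of 100: 19.7 points
- n = 36 of 100: 13.1 points
- n = 93 of 333 (equal thirds): 8.6 points

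Stratifying removes the drift between about 13 and 20 points. The centre stays near 16.

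**6. Leaving surgeons out.** Take the same equal thirds and rates as in step 3. If surgeons are the highest group, the other two average (40 + 50)/2 = 45%, (30 + 50)/2 = 40% or (20 + 50)/2 = 35%. Against 50%, these are shifts of 5, 10 or 15 points. The shift has the opposite sign if surgeons are the lowest group and is zero if they are the middle one. In the mildest unequal case it already equals the whole planned half-width.

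**The case against.** A reader might infer that the study compares specialties, institutions and ranks, and that an unstratified list therefore throws away precision for no saving. The documents do not support this.

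- Institutions appear only as settings and ranks only as eligibility. The hypothesis and primary outcome concern doctors as a whole, and no between-group test is named. A specialty comparison rests on the word used in the design sentence, and the sample-size section uses the same word for a single pooled 50%, where it can only mean among. A comparison is at most implied.
- The text does not say that there is one list or that it is unstratified. That is inferred from silence, although the sample-size formula points the same way.
- 278 meets the plan's own pooled target, and the gain from strata is small unless specialties differ widely. Post-stratified analysis would recover most of it.
- The wide interval in a small specialty comes from its size. Proportional allocation leaves it near ±16 points. Only oversampling with weights or a larger sample would narrow it.
- Drawing in proportion does not remove true differences in rank between specialties, and with an online questionnaire it controls who is invited, not who replies.
- Low cost assumes a staff list that carries specialty and hospital, which the documents do not describe.

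All of these stand, and they limit the size of the point. They do not answer the omission of surgeons from the sampling sentence, and they give no reason to leave the mix of invitees to chance when the same 278 can be drawn in proportion.

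**Conclusion.** The point holds in a limited form. The sampling sentence contradicts the aim, the eligibility criteria and the 1000 by leaving out surgeons. With no strata stated, the specialty and hospital mix of those invited is left to chance. The omission of surgeons is the more serious half: under the assumed rates it shifts the pooled percentage by 0 to 15 points, depending on where surgeons lie.

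The stratification half is modest. It takes the pooled half-width from 5.0 to between 4.4 and 4.9 points, and it gives a settled count of about 28 in place of 20 to 36 for an assumed specialty of 100. It does not make small-specialty results precise. Every figure other than the 278 and its 5.0 points rests on assumed specialty sizes or rates and on full response. The change is worth making before the sample is drawn, because it cannot be made afterwards.

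**What to change.** 1. Define the frame as all three specialties at both institutions. Rewrite the sampling sentence to include cardiothoracic surgeons, and say which staff lists supply each group.
2. Split the frame by specialty and hospital (3 × 2 = 6 strata) and draw the 278 at random in proportion to stratum size.
3. Record specialty, hospital and rank on the questionnaire.
4. Estimate the overall percentage with a stratified variance, and weight to the stratum sizes if response differs between strata.
5. State that ±5 points applies only to the pooled percentage, and give any specialty result its own 95% interval. If specialty comparisons are intended, say so and decide whether small groups need oversampling.

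**Cost.** No extra participants. The staff list must carry specialty and hospital, the form gains three items, and the estimator is slightly more complex.
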